## 1.1.3 Exploratory Objectives

- To determine the incidence of anti-moxetumomab antibodies after combined treatment.
- To determine the plasma levels of moxetumomab pasudotox-tdfk with combined treatment.
- To determine the effects of combined therapy on normal B and T-cells.

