Of 32 patients at 50 mcg/kg QOD x3 evaluated for neutralizing (antidrug) antibodies, 24 (75%) had >50% neutralization of 200 ng/ml, and 17 (53%) had >75% neutralization of 1000 ng/ml of moxetumomab pasudotox-tdfk. Since CR duration was higher with compared to without consolidation cycles of moxetumomab pasudotox-tdfk (p=0.0004), and since early immunogenicity prevented consolidation cycles, prevention of immunogenicity is an important goal in immunotoxin treatment of HCL [9]. Further analysis of response vs immunogenicity, reported in the supplemental section of phase I report [9], showed trends for higher MRD-negative CR rate (8 of 15 vs. 3 of 17; P = .06) and longer CR duration (median undefined vs. 19.1 months, P = .05) in patients without vs. with antibodies neutralizing more than 75% of the activity of 1000 ng/ml of moxetumomab pasudotox-tdfk. Pharmacokinetic analysis in this report showed that despite early neutralizing antibodies which made patients ineligible for future cycles (>50% neutralization of 200 ng/ml), we could observe increases in peak level and area under curve (AUC), and decreases in volume of distribution and clearance, from the 1st dose to the 3rd dose of the last cycle. This indicated that even secondary immunogenicity with moxetumomab pasudotox-tdfk in

Version Date: 04/16/2025

HCL was too weak to prevent titration of antidrug antibodies by repeated dosing. This make it possible that an agent like rituximab, which could not prevent immunogenicity in solid tumors [13] receiving a large immunotoxin chemical conjugate, may prevent it in HCL patients with impaired immune system receiving a smaller recombinant immunotoxin.

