- 1. End of treatment visit will occur 28-42 days after 1st dose of last cycle.
- All participants will be offered the opportunity to complete an NIH advance directives form (Section 12.3). This should be done preferably at baseline but can be done at any time during the study. The completion of the form is strongly recommended but not required.
- Within 4 weeks prior to enrollment, could be combined with pre cycle 1. Only anti-moxetumomab pasudotox-tdfk antibodies will be assessed.
- 4. CBC + Diff should be done every 3 months until 2.5y after EOT, then every 6 months.
-  Follow-up time points not requiring restaging are 1, 2 and 3.5 years after EOT, then every 2 years
- 6. Restaging requiring imaging, labs (and bone marrow if CR suspected) is 1.5 and 2.5 years after EOT, then every 2 years.
- Within 6 months of initiation of study therapy provided within 4 weeks after last therapy. Baseline HLA may be done anytime.
- PK and PK bioassay Time points: On days 1 and 5 of cycles 1,2,3,5,7. For cycles 1 and 2: pre, and immediately post, +/- 8 min, then 30+/-10, 60+/-15, 180+/-20,, and 360+/-50 minutes after moxetumomab pasudotox-tdfk end of infusion; On cycles 3, 5, and 7: pre and post infusion, 1-8 min; on cycles 4, 6, and 8 no PK will be drawn. Each ~6cc in K2EDTA tubes.
- 9. CT Neck-Pelvis is done at baseline to identify sites of disease, including spleen, and at EOT and restaging points MRI of these sites may be substituted. In asplenic participants without baseline sites of disease, MRI of the abdomen may be done at restaging time points. The entire neck to pelvis CT need not be repeated if the disease (splenomegaly) was contained within just the abdominal or abdominal-pelvis levels of the CT. Pre-cycle scans will only be performed if participant is being restaged.
- 10. Deviations on post-EOT time points may be +/- 2 months until 2.5 years and +/- 4 months thereafter.
- Chemistries includes sodium, potassium, chloride, bicarbonate, creatinine, glucose, blood urea nitrogen (BUN), albumin, calcium, magnesium, phosphorus, AST (SGPT), ALT (SGOT), total bilirubin, direct bilirubin, lactate dehydrogenase (LDH), total protein, alkaline phosphatase, creatine kinase (CK or CPK), and uric acid. Except on day 15. Day 15 only acute care panel along with CBC with c diff and urine analysis will be required.
- 12. Optional when not performed at NIH
- 13. +/-1 day,

Version Date: 04/16/2025

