## **Step 7: Administration**

- Infuse the diluted LUMOXITI solution intravenously using early call back/reverse flow method over 30 +/- 5 minutes.
- **Do not** mix LUMOXITI, or administer as an infusion with other medicinal products.
- After the infusion, flush the intravenous administration line with of 0.9% Sodium Chloride Injection, USP at the same rate as the infusion. This ensures that the full LUMOXITI dose is delivered.

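### The post-dose PK sample has a two-sided window in cycles 1 and 2 but a post-only window in cycles 3, 5 and 7, so early-cycle peaks may be understated

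*Combined protocol and SAP*

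**What the plan says.** Section 1.1.3 lists an exploratory objective: "To determine the plasma levels of moxetumomab pasudotox-tdfk with combined treatment". Footnote 8 in Section 3.4 gives the sampling times, on days 1 and 5 of cycles 1, 2, 3, 5 and 7.

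- **Cycles 1 and 2:** "For cycles 1 and 2: pre, and immediately post, +/- 8 min, then 30+/-10", followed by samples at 60, 180 and 360 minutes with windows of 15, 20 and 50 minutes either side. Times run from the end of the moxetumomab infusion.
- **Cycles 3, 5 and 7:** "On cycles 3, 5, and 7: pre and post infusion, 1-8 min". There are no later samples.
- **Other cycles:** "on cycles 4, 6, and 8 no PK will be drawn".

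Appendix C, Step 7 sets the infusion: "Infuse the diluted LUMOXITI solution intravenously using early call back/reverse flow method over 30 +/- 5 minutes". It continues: "After the infusion, flush the intravenous administration line with of 0.9% Sodium Chloride Injection, USP at the same rate as the infusion", and gives the reason: "This ensures that the full LUMOXITI dose is delivered". The supplied text does not say whether the end of infusion in footnote 8 means the end of the bag or the end of this flush.

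Section 6.2.1 provides for recording the timing of drug administration. The supplied text does not require actual PK draw times to be recorded. Section 5.2.1 leaves the handling of PK samples to a Lab Manual that is not among the documents. Section 10.4.6 makes exploratory analyses descriptive.

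**The concern.** The same quantity, the level just after dosing, is collected under two rules, and only the cycle 1-2 rule can reach back into the infusion. A sample taken while drug is still running in is not a peak. Any error from that source pushes the cycle 1-2 value down and has no counterpart in cycles 3, 5 and 7.

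This matters because exposure over repeated cycles is the natural question for these data. Section 1.2.1 reports from the phase 3 trial that antibody titre rose with repeated cycles and that drug exposure was reduced at high titre. The anti-CD20 antibody is added partly to limit immunogenicity. In cycles 3, 5 and 7 the single post-infusion sample is the only post-dose level. If the early-cycle reference is too low, a later fall can look like preserved exposure. With at most 26 participants, a few mistimed samples would not average out.

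**Working it through.** The plan states no figure that depends on this window, so there is none to reproduce.

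**Inputs from the documents.** Infusion duration T = 30 minutes, range 25 to 35 (Appendix C, Step 7). Post-dose window −8 to +8 minutes in cycles 1 and 2, and +1 to +8 minutes in cycles 3, 5 and 7 (footnote 8).

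**Assumptions.** Constant infusion rate, one compartment, half-life 0.5 to 8 hours. No half-life is stated, so a range is used.

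**Step 1: which windows can reach into dosing.** The earliest permitted times for the later samples are 30 − 10 = 20, 60 − 15 = 45, 180 − 20 = 160 and 360 − 50 = 310 minutes after the end. Only the first post-dose sample can fall before it, at 0 − 8 = −8 minutes.

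**Step 2: share of the infusion given by −8 minutes.** This is (T − 8)/T: 17/25 = 68.0%, 22/30 = 73.3%, 27/35 = 77.1%.

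**Step 3: level sampled relative to the end-of-infusion level, T = 30.** With k = ln 2 / half-life in minutes:

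- before the end: (1 − exp(−22k)) / (1 − exp(−30k)) at −8 minutes
- after the end: exp(−kd) at +d minutes

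Example at a half-life of 60 minutes: k = 0.01155, so the first ratio is 0.2244/0.2929 = 0.766.

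| Assumed half-life | −8 min | +1 min | +8 min |
|---|---|---|---|
| 30 min | 0.797 | 0.977 | 0.831 |
| 60 min | 0.766 | 0.989 | 0.912 |
| 120 min | 0.750 | 0.994 | 0.955 |
| 240 min | 0.742 | 0.997 | 0.977 |
| 480 min | 0.738 | 0.999 | 0.989 |

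A draw at −8 minutes is therefore 1 − 0.797 = 20% to 1 − 0.738 = 26% too low.

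**Step 4: early against later cycles.** Suppose true exposure does not change, the early sample is drawn at −8 minutes and the later one at +1 to +8 minutes. The ratio of early to later reading is then 0.797/0.977 = 0.82 to 0.797/0.831 = 0.96 at a 30-minute half-life, and 0.742/0.997 = 0.74 to 0.742/0.977 = 0.76 at 240 minutes. The artefact is smallest with a short half-life and a late later-cycle draw.

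**Step 5: AUC.** Serial samples exist only in cycles 1 and 2. With half-lives of 30 to 240 minutes, a −8 minute draw changes the linear-trapezoid AUC, to the 360-minute sample, by −3% to −9% if analysed at nominal time and by −2% to −6% at actual time.

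**Step 6: the flush.** At an illustrative 70 kg and 40 mcg/kg, with drug reconstituted at 1 mg/mL, the bag holds 50 + 1 + 2.8 = 53.8 mL, a rate of 53.8/30 = 1.79 mL/min. Line volume is not given. An assumed 5 mL would hold 5/53.8 = 9% of the dose and clear in 2.8 minutes; 25 mL would hold 46% and clear in 13.9 minutes. This applies to every cycle.

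**The case against.** The strongest reply is that the cycle 1-2 sample is described as immediately post, in a list timed from the end of infusion, so a draw during dosing was never meant. That is a fair reading. It makes the minus sign an ambiguity to correct, and nothing in the documents shows that any sample was drawn early. The 20% to 26% applies only at the extreme limit. A post-only window is also imperfect: at a 30-minute half-life, +8 minutes reads 83%. These points limit the size of the concern. They do not justify keeping two rules for one sample.

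Three stronger readings are tempting, and the documents do not support them.

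- **AUC is not comparable across cycles.** Cycles 1 and 2 share one window. Cycles 3, 5 and 7 yield no comparable AUC because they have only pre and post samples, whatever the window.
- **The flush makes cycles non-comparable.** Step 7 applies to every dose, and the size of its effect rests on an unstated line volume. The named early call back/reverse flow method is not defined and may also bear on line handling. What remains is an undefined time zero.
- **The first-to-third-dose comparison in Section 1.2.1 is compromised.** There an earlier trial reports that "we could observe increases in peak level and area under curve (AUC" rose from the first to the third dose of the last cycle. That comparison is within one cycle. Here days 1 and 5 of any PK cycle share a window, so the rules create no systematic difference, although variable timing could add noise.

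It is also true that the stakes are modest. No peak or AUC endpoint, test or decision rule is specified for this trial, and immunogenicity is measured directly (Section 5.2.2).

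**Conclusion.** The inconsistency is real. Read literally, the cycle 1-2 rule permits a draw with about 73% of a 30-minute infusion given, reading 20% to 26% below the end-of-infusion level. This rests on a one-compartment, constant-rate model and an assumed half-life of 0.5 to 8 hours. The early-cycle peak may be understated relative to cycles 3, 5 and 7; whether it is depends on actual draw times, which the supplied text does not require to be kept. The finding concerns the peak only. The meaning of end of infusion relative to the flush needs clarifying for all cycles. Priority is low, because PK is exploratory and descriptive.

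**What to change.** - In footnote 8, give the first post-dose sample in cycles 1 and 2 the window already used in cycles 3, 5 and 7: 1 to 8 minutes after the end of infusion.
- Record actual infusion-end, flush-end and draw times for every PK sample, and analyse by actual time.
- For samples already collected, use actual times where they exist, and flag in peak summaries any drawn before the infusion ended.
- State whether the end of infusion includes the Appendix C, Step 7 flush, and keep one time zero for all participants. Twelve were enrolled by 9/24/21 (Section 3.1.4), so changing time zero partway would create a new inconsistency, and past flush-end times may not be available.

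The cost is a footnote edit and a few recorded times, with no added visits, samples or blood. A few existing early samples may drop out of the peak summary.

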## 3.5 COST AND COMPENSATION

## 3.5.1 Costs

NIH does not bill health insurance companies or participants for any research or related clinical care that participants receive at the NIH Clinical Center. If some tests and procedures are performed outside the NIH Clinical Center, participants may have to pay for these costs.

## 3.5.2 Compensation

Participants will not be compensated on this study.

#### 3.5.3 Reimbursement

The NCI will cover the costs of some expenses associated with protocol participation. Some of these costs may be paid directly by the NIH and some may be reimbursed to the participant/guardian as appropriate. The amount and form of these payments are determined by the NCI Travel and Lodging Reimbursement Policy.

## 3.6 CRITERIA FOR REMOVAL FROM PROTOCOL THERAPY AND OFF STUDY CRITERIA

Prior to removal from the study, effort must be made to have all participants complete a safety visit approximately 28-42 days following the last dose of study therapy.

## 3.6.1 Criteria for removal from protocol therapy

- Completion of study therapy
- Progressive disease or DLT
- HUS
- Unacceptable toxicities as described on Sections 3.1.2 and 3.3.
- Intercurrent illness or medical circumstances, including uncontrolled infection at the discretion of the primary investigator
- Radiation therapy or other treatment for HCL other than splenectomy
- Voluntary withdrawal from the treatment regimen
- PI determines further treatment on this study is not in participant's best interest
- Participants who are off-treatment but still on-study will be followed as per the schedule in Section 3.4, until they begin alternative therapy or voluntarily withdrawal from follow-up testing. Thereafter, they may be followed on-study for survival and other secondary endpoints.
- Positive pregnancy test

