# 2.2.1.1.4 Within 3 days before starting drug

Pregnancy test (urine or serum). Women of childbearing potential must have a negative pregnancy test

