## 3 STUDY IMPLEMENTATION

## 3.1 STUDY DESIGN

This is a Phase 1 trial, two-arm, non-randomized trial involving the administration of moxetumomab pasudotox-tdfk 30-40 mcg/kg iv and rituximab/Ruxience 375 mg/m² iv, 50-400 mg/hr. The purpose of the rituximab/Ruxience is to decrease the HCL tumor burden, allowing the

Version Date: 04/16/2025

63 kDa immunotoxin to reach all the malignant cells, thereby facilitating tumor eradication, and prevention of neutralization of the immunotoxin by the immune system, through the action of rituximab/Ruxience on normal B-cells. To allow sufficient time for the rituximab/Ruxience to act prior to moxetumomab pasudotox-tdfk, in the first cycle, rituximab/Ruxience will be given on day -2 followed by moxetumomab pasudotox-tdfk on days 1, 3 and 5. Thus on cycle 1 only, moxetumomab pasudotox-tdfk will begin on the 3rd day after rituximab/Ruxience. On subsequent cycles, spaced ~ 4 weeks (as few as 25 days) apart, rituximab/Ruxience will begin on day 1 and moxetumomab pasudotox-tdfk on days 1, 3 and 5. Participants will receive up to 4 cycles past documentation of CR without MRD, up to a maximum of 8 cycles which means, no participant in this trial will receive more than 8 cycles.

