Please refer to Appendix C for information related to moxetumomab pasudotox-tdfk administration and preparation. Handle moxetumomab pasudotox-tdfk with caution to avoid skin and mucus membrane contact, aerosol formation, or ingestion. Monitor participants for infusion reactions, CLS, TLS, and thrombotic microangiopathy/HUS. To monitor for HUS, before every infusion, hemoglobin levels, platelet count, and serum creatinine will be checked. If HUS is suspected, blood LDH, indirect bilirubin, blood smear schistocytes for evidence of hemolysis will be promptly checked. Appropriate supportive measures will be taken, including fluid repletion and hemodynamic monitoring. Hospitalization should be considered if clinically indicated. If participants develop HUS, moxetumomab pasudotox-tdfk will be discontinued. To monitor for CLS, it is recommended that before every infusion, participants' weight and blood pressure are checked. CLS will be considered if participant's weight has increased by 5.5 pounds (2.5 kg) or ≥5% from day 1 of each cycle and the participant is hypotensive. Peripheral edema, hypoalbuminemia, and respiratory symptoms, including shortness of breath and cough, will be checked. If CLS is suspected, decrease in oxygen saturation, evidence of pulmonary edema, and/or serosal effusions will be checked. Appropriate supportive measures, including administration of concomitant corticosteroids PO or IV, will be used. Hospitalization will be considered if clinically indicated.

Vital signs will be obtained every 15 ( $\pm$  10) minutes during the moxetumomab pasudotox-tdfk infusion, then every hour ( $\pm$ 30 minutes) for an additional 4 hours during Cycle 1. During subsequent cycles, vital signs will be obtained as indicated in the **Study Calendar**. Weight, CBC + Diff, chemistries and urinalysis will be assessed prior to each infusion of moxetumomab pasudotox-tdfk.

To mitigate risk for allergic reaction and fever, participants will be premedicated with acetaminophen and famotidine, as indicated in Section 3.2.3. Substitutions of cimetidine for famotidine is permitted. In participants experiencing infusion-related reactions, including, but not limited to pyrexia, nausea, or dyspnea, premedication with dexamethasone and/or diphenhydramine intravenous (IV) or oral may be administered at the investigator's discretion as secondary prophylaxis.

Version Date: 04/16/2025

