#### 3.3 DOSE MODIFICATIONS

Dosing may be delayed up to 4 months for toxicity or logistical reasons, including the inability of the participant to get to the clinic. Treatment cycles need not be delayed for cytopenias but must be delayed for participants in CR presenting grade 3 cytopenia, for grade 3-4 infections and for grade 3-4 neutropenia combined with fever. Any grade >3 infection not resolving within the 4 week delay will be considered DLT.

If participants develop grade 2 CLS, dosing will be delayed until recovery of symptoms; if CLS grade  $\geq$ 3 develops, moxetumomab pasudotox-tdfk will be discontinued.

Any occurrence of DLT as defined in Section 3.1.2 will result in removal from study therapy.

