# 3.4 STUDY CALENDAR

						All cycles  (1 cycle=28 days)					
Procedure	Screen/ Baseline	Pre- Cycle 	Cycle 1 Day -2 	Cycle 1 Day -1 	Days 1-5	Day 8	Day 15±3	EOT 	EOT +	F/U 	Restage 
History & PE	X 	X 						X	6m 		X
Vital signs including pulse oximetry 	$X^3$	$X^{20}$			X 	X		X	Λ		Λ
Performance Score	$X^3$	$X^{20}$			Λ	Λ		Λ			
CBC + Diff	$X^3$	X 	X	X	X	X	X	X	X	X 	X
Weight	X	X	71	71	71	X	21	21	21	71	71
Chemistries  , urinalysis	$X^3$	X 	X 	X 	X	X	X	X	X	X 	X
D-Dimer, Fibrinogen, Ferritin, PT/INR, PTT, amylase, lipase, GGT, IgA, IgG, IgM, CRP, haptoglobin	X 	X 	X 	X 	A	X 	A	X	X	A	X
Reticulocyte count, VWF antigen, VWF activity, PAI-1, FDP, p-selectin, thrombomodulin			X	X							
Cytokine panel 13 			X	X							
Immunofixation electrophoresis (IFE) and TBNK	X	X 				X		X	X		X
Flow cytometry	X 	X 						X	X	X	X
EKG	X 	X 						X	X		X
Lipid panel, TSH, FT4, FT3, T4, T3, SPEP	X 							X	X		X
HBcAB, HBsAg, HIV test	X 										
Pregnancy test (females < 50 years)	X 										
24hr urine protein and creatinine	X 					X 					
NIH Advance Directives Form 	X										
CT Neck-pelvis or MRI 	X 	X						X	X		X
MRI C & T-spine 	X 	X						X	X		X

Version Date: 04/16/2025

Echo, PFTs, stress test, abdominal U/S, HLA	X 										
Adverse Events 	X	X						X			
Concomitant Medications 	X 	X						X	X		
Correlative Studies 		(F	lease refer	to Section I	Error! R	eferen	ce source	not fou	nd.)		
BMBx & BMA w/flow and PCR	X 	X 						X	X		X
Blood PCR	X	X						X 	X 		X 
PaxGene RNA & DNA	X 	X						X	X	X	X
Biomarker	X 	X				X		X	X	X	X
ADAs 	X				X 			X	X 		
PBMCs	X 										
Urine (renal proximal tubule cell		X			X 	X					
damage)		$\Lambda$			Λ	$\Lambda$					
PK and PK bioassay 					X 						

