- To be done at bone marrow time points, to correlate the status of the BMBx with the vertebral BMA signal by MRI. May be cancelled at the discretion of the PI, including if participant unable to get MRI at NIH and not covered by insurance outside NIH.
- 15. This test will be conducted within 3 days prior to enrollment
- 16. Performed within 4 weeks before initiation of study therapy.
- Adverse events and concomitant medications will be monitored continuously in every visit.
- 18. Samples collected during the course of this study will be stored, tracked, and disposed of as specified in investigator's companion protocol, 10C0066, on which all participants will be co-enrolled.
- During the moxetumomab pasudotox-tdfk infusion, vital signs will be obtained every 15 (±10) minutes, then every hour (±30 minutes) for an additional 4 hours during Cycle 1. During subsequent cycles, vital signs will be obtained every 15 (±5) minutes during the moxetumomab pasudotox-tdfk infusion, then every hour (±30 minutes) for an additional 2 hours. Vital signs will also be obtained on Day 8 ± 1 day for the first 3 dosing cycles.
-  May be done up to 3 days prior to day 1 of cycle.
- Must be done on day 1 of cycle 1 prior to treatment.
- 22. Cycle interval may be shortened to 25-27 days due to logistical reasons.
-  Pre-cycle tests may be done 0 to 2 days before and maybe combined with either baseline for cycle 1 or day 1 or both.
- 24. During rituximab/Ruxience infusion on cycle 1 day -2 vital signs will be obtained with every dose change and as needed.
- 25. Must be completed on day 8 but may be cancelled at PI discretion.
- 26. Pre-cycle and pretreatment on days 3, 5, and 8.
- 27. Pre-cycle bone marrow and scans to be done at the discretion of the PI based on the participants HR status.
- 28. Sampling pre-dose before cycles 1,2,3,5, and 7.
- 29. Sampling at 3 and 6 months after the end of treatment evaluation.
- 30. Sampling in case HUS or CLS are observed.
- 31. Cycle 1 IFE to be done pre cycle may be combined with baseline labs +/- 1-4 days and again pre moxetumomab pasudotox-tdfk on Cycle 1 day1.
- 32. Screening labs can be combined with pre cycle 1 labs if done within 5 days of day -2 with the exception of the labs listed as day -2 labs

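### No pregnancy test is scheduled for cycles 2-8, although a positive test ends therapy: a minor, low-frequency safety gap with a cheap fix

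*Combined protocol and SAP*

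**What the plan says.** **Testing.** The Study Calendar (Section 3.4) has one row for this, "Pregnancy test (females < 50 years", with a single mark under Screen/Baseline. Its footnote 15 reads "This test will be conducted within 3 days prior to enrollment". Section 2.2.1.1.4 covers the same test, timed to the 3 days before starting drug: "Women of childbearing potential must have a negative pregnancy test". The Pre-Cycle, on-treatment, end-of-treatment and follow-up columns are blank, and no other section schedules a test.

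**Exposure.** Section 3.1 sets the limit: "no participant in this trial will receive more than 8 cycles". Section 2.1.2.3 excludes pregnant women because both agents may be teratogenic or abortifacient.

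**Action on pregnancy.** Section 3.6.1 lists "Positive pregnancy test" among the criteria for removal from therapy. Section 8.5.1 requires immediate discontinuation, with a report to the sponsor within 24 hours of the investigator becoming aware.

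**Existing safeguards.** Section 2.1.1.8.1 requires highly effective contraception (failure below 1% a year when used consistently and correctly) during the study and for 12 months after the antibody, and asks a woman who is or may be pregnant to tell her physician at once. The calendar also marks a history and physical examination before each cycle.

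**The concern.** The removal rule turns on a test result, but once treatment has begun no scheduled test would produce one. Contraception prevents most pregnancies, and self-report or clinical suspicion will find those that someone suspects. Neither finds a pregnancy that nobody suspects. Followed as written, the plan could give another cycle to a woman in that position.

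What is at stake is the safety of the woman and fetus. No endpoint, dose-limiting-toxicity rule, sample size or analysis depends on it.

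**Working it through.** The plan gives no figure on this point to reproduce. The check compares the calendar with the stopping rules, then sizes the gap.

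**1. Length of the untested period.**
- Cycles with no scheduled test: 8 - 1 = 7.
- Day 1 of cycle 1 to day 1 of cycle 8: 7 x 28 = 196 days, or 7 x 25 = 175 days at the shortest interval the calendar allows.
- Section 3.3 can lengthen this: "Dosing may be delayed up to 4 months for toxicity or logistical reasons".

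**2. Expected number of women.** The phase 3 trial described in Section 1.2.1 enrolled 17 women among 80 patients, with a median age of 60. Applied to the 26 evaluable participants planned in Section 10.2: 26 x 17/80 = 5.525 women. The documents do not give the share under 50. Assuming 10-25%: 0.10 x 5.525 = 0.55 and 0.25 x 5.525 = 1.38 women.

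**3. Expected pregnancies followed by further dosing.** The formula is women at risk x annual failure rate x window in years. The rate is 1%, taken from Section 2.1.1.8.1, and the window is 196/365 years with no delays.

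- 10% of women under 50: 0.5525 x 0.01 x 196/365 = 0.0030
- 25% under 50: 1.381 x 0.01 x 196/365 = 0.0074
- 50% under 50: 2.7625 x 0.01 x 196/365 = 0.015
- All 5.525 women: 5.525 x 0.01 x 196/365 = 0.030

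**4. Participants a change could still reach.** Section 3.1.4 reports 12 enrolled by 9/24/21, leaving 26 - 12 = 14 of the 26. Then 14 x 17/80 = 2.975 women. At 10-25% under 50 that is 0.30 to 0.74 women, giving 0.0016 to 0.0040 expected pregnancies. This version is dated 04/16/2025 and does not state accrual, so the number still to be dosed may be smaller.

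**5. How firm these figures are.** They are not bounds. The 1% rate assumes correct use, and permitted delays lengthen the window; both would raise the result. Shorter cycles, fewer cycles and women who are not sexually active would lower it.

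**6. What a pre-cycle test would achieve.** A conception too recent to detect at one test would generally be found at the next, 25 to 28 days later. Further dosing would then be limited to about one cycle, that is 3 moxetumomab doses and 1 antibody dose. The documents state no detection lag, so this is a judgement.

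**7. Which urine specimen.** Section 3.2.1 says "chemistries and urinalysis will be assessed prior to each infusion", but this refers to moxetumomab infusions. In cycles 2-8 the antibody is given first on day 1, so that wording does not guarantee a specimen before the first drug. The calendar separately marks urinalysis in the Pre-Cycle column, and footnote 23 gives the window: "Pre-cycle tests may be done 0 to 2 days before". That specimen meets the need.

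**The case against.** The strongest case against is that the risk is already controlled in layers: a negative test before treatment, mandatory highly effective contraception with weak methods barred, self-report, a pre-cycle history and examination, and immediate discontinuation on pregnancy. The removal criterion works with any test done on suspicion. The expected count is a few thousandths, about 0.03 even if every expected woman could conceive, and enrolment may be largely complete.

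Most of this stands, and it is why the point is minor. It does not close the gap, because none of the layers after baseline detects a pregnancy that is unsuspected.

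A reader might infer more than the documents support:

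- **That the plan contradicts itself.** It does not. No section promises repeat testing, and none bars an unscheduled test.
- **That a pre-cycle test would remove fetal exposure.** It would not. Section 1.2.1 regards rituximab as likely still present in patients treated within the previous 6 months, and describes B-cell depletion for at least 6 months after the last dose. Contraception remains the control for that exposure.
- **That Section 3.3 already provides for holding a dose while a result is checked.** It allows delays for toxicity or logistics, and a pending pregnancy result is not clearly either.
- **That a positive urine result should await serum confirmation before removal.** Section 3.6.1 has no confirmation step and Section 2.2.1.1.4 accepts urine or serum, so this would change the criterion.

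**Conclusion.** The point holds as a minor, low-frequency safety improvement. The single pre-treatment test leaves up to 7 cycles without a scheduled one, and the plan as written could re-dose a woman with an unsuspected pregnancy.

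The expected number of such pregnancies is roughly 0.003 to 0.007 among 26 participants. That rests on the phase 3 sex ratio, an assumed 10-25% of women under 50, 1% annual contraceptive failure and no dosing delays. The case for acting rests on the seriousness of the harm and the very low cost of the change, not on frequency. If no woman of childbearing potential remains to be dosed, the change has no practical effect in this trial.

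**What to change.** In the Study Calendar, mark a urine pregnancy test in the Pre-Cycle column for cycles 2-8, for women of childbearing potential. Add a footnote saying that:

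- it is run on the pre-cycle urinalysis specimen, within the existing 0 to 2 day window;
- the result must be known before the first drug of the cycle, which is rituximab or Ruxience on day 1;
- a positive result stops dosing under Section 3.6.1, whose wording is unchanged.

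The contraception and 12-month pregnancy follow-up requirements stay as they are.

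The cost is one calendar entry, one footnote and at most 7 inexpensive urine tests per affected woman. At 0.55 to 1.38 women that is about 4 to 10 tests in all (7 x 0.55 = 3.9; 7 x 1.38 = 9.7). No new visit, staff or invasive procedure is needed. The downside is an occasional false positive, which would stop dosing under the rule as it stands.
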